**Impact of The Real Cost Vaping Prevention Advertisements on Adolescents**

**Protocol**

**NCT #04836455**

**Version Date: 5/27/2021**

## Participants

We recruited adolescents living in the United States (US) from online panels administered by Qualtrics. Eligibility criteria were: aged 13 through 17 years, able to read and speak in English, able to take an online survey in English, and susceptible to e-cigarette use as shown by an answer of 2 or greater on any of five e-cigarette susceptibility items. The susceptibility items assessed the extent to which adolescents were open to vaping, with a 4-point response scale that ranged from “definitely not” (coded as 1) to “definitely yes” (4).

Our target sample size was 1,500, which accounted for up to 33% of participants dropping out during the trial. With an estimated intraclass correlation of .70, the trial had power to detect an effect size of  $d=.25$  or larger between intervention arms (combined) and the control arm.

Recruitment took place from September to November 2021. Legal parents or guardians provided informed parental consent online, and adolescents provided assent online before beginning the surveys. Of the 1,708 adolescents who met inclusion criteria, 151 declined to participate and 43 were screened but unable to enroll because the study quota had been met (Figure 1). This trial was approved by the University of North Carolina Institutional Review Board and is registered at [clinicaltrials.gov](https://clinicaltrials.gov/ct2/show/NCT04836455), identifier NCT04836455 (<https://www.clinicaltrials.gov/ct2/show/NCT04836455>). This paper follows CONSORT reporting guidelines for RCTs.

## Procedures

*Trial design and protocol.* We conducted a three-arm RCT with parallel assignment. Adolescents participated in four weekly online visits over a three-week period, completing a survey at each visit. Exposures to campaign ads occurred at Visits 1, 2, and 3. At the start of the

trial (Visit 1), participants were randomized to see a series of ads from one of two FDA *Real Cost* vaping prevention ad trial arms (health harms or addiction) or to a control arm (investigator-created neutral videos about vaping). Qualtrics software used simple randomization based on a single allocation ratio. Participants were randomized without replacement to one of the three trial arms using the Qualtrics randomizer. In each trial arm, participants viewed the same three ads per session, in a random order, corresponding to the trial arm they were assigned. Participants were told they were going to view three short ads, but received no information on the content or number of arms. The research team was not blinded after assignment because interventions were administered online.

At each of the visits (Visits 1 – 4), participants completed surveys reporting primary and secondary outcomes. Participants received incentives in the form of points for taking the surveys, with a total cash equivalent of \$35 after completing the trial (\$5 for the first and second surveys, \$10 for the third survey, and \$15 for the final survey). A pilot study with 51 participants was conducted prior to the trial to test trial procedures.

*Intervention messages.* Participants in both intervention trial arms viewed three 30-second ads from the *Real Cost* campaign, corresponding to one of the two major themes of the campaign. Those in the health harms trial arm viewed ads about toxic substances and lung damage, while those in the addiction trial arm viewed ads about consequences of nicotine addiction. Those in the control arm viewed three 30-second investigator-created neutral videos about vaping consisting of black text on a white screen with a narrator reading the text. The content of these ads included product definitions, farming practices, and manufacturing practices adapted from Wikipedia and other sources (see the Table 1).

## Measures

At the first session (Visit 1), each participant reported vaping and smoking behaviors in the survey, then viewed ads that corresponded to their trial arm. They completed measures assessing message reactions after viewing each ad, after which they completed measures of susceptibility to vaping and smoking, vaping and smoking beliefs, and demographics. For the subsequent weeks of the trial (Visits 2 and 3), participants completed surveys with measures of susceptibility to vaping and smoking, vaping and smoking beliefs, and vaping and smoking behavior. Then, they viewed the same three ads from their trial arm and completed the message reactions items. At Visit 4, participants completed surveys assessing susceptibility to vaping and smoking, vaping and smoking beliefs, and vaping and smoking behavior (eFigure 1 in the Supplement).

**Primary outcome.** Susceptibility to vaping at Visit 4 was the primary trial outcome. Susceptibility prospectively predicts vaping behavior, including as a scaled score where higher values predict both greater initiation and current use of vapes. We assessed susceptibility with a 3-item susceptibility to vaping scale, similar to other studies. This scale assesses the extent to which adolescents are open to vaping, with a 4-point response scale ranging from “definitely not” (coded as 1) to “definitely yes” (coded as 4) (eTables 2 and 3 in the Supplement). We calculated a susceptibility score by averaging the 3 items, with higher scores representing higher susceptibility (Cronbach’s  $\alpha=.93$ ). Susceptibility was measured *after* ad exposure at Visit 1 to capture immediate ad impact and *before* ad exposure at Visits 2-4 to capture ad impact over time.

**Secondary outcomes.** The survey assessed several secondary outcomes hypothesized to elicit behavior change. Response scales for most secondary outcomes had five points, coded such

that higher scores represented a greater amount of the construct. For multi-item scales, overall scale scores were of the average of the items.

*Message reactions.* A single item assessed attention to the message and a 3-item scale assessed negative affect ( $\alpha=.83$ ). Message reactions were measured immediately following ad exposure. These measures were last assessed at Visit 3 because the ads were not shown at Visit 4.

*Vaping outcomes.* Three-item scales assessed cognitive elaboration ( $\alpha=.92$ ), social interactions ( $\alpha=.94$ ), vaping health harm risk beliefs ( $\alpha=.92$ ), vaping addiction risk beliefs ( $\alpha=.89$ ), and vaping attitudes ( $\alpha=.91$ ). Participants reported the number of days they vaped over the past 7 days at each visit. These outcomes were measured *after* ad exposure at Visit 1 and *before* ad exposure at Visits 2-4, except for days vaped which was always measured before ad exposure.

*Smoking outcomes.* Single items assessed smoking health harm risk belief, addiction risk belief, and smoking attitude. Susceptibility to smoking was assessed with a 3-item scale ( $\alpha=.95$ ). Participants reported the number of days they smoked over the past 7 days at each visit. We chose to retain the continuous measures of number of days vaping and smoking rather than dichotomizing these outcomes (as proposed in our trial registration) because we found substantial variability in number of days that these products were used.

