The investigators plan to enroll 500 individuals per trial arm with the expectation that as many as 33% of participants will drop out of the study before week 3 follow-up. The investigators will use a FIML estimator so the investigators can retain all available data, including observed repeated measures from participants who go on to drop out of the study. With an estimated ICC=.7 (and thus a design effect of 2.4), the investigators have statistical power to detect an effect as small as Cohen's $d = .25$. This effect size is around the same magnitude as the effects observed with pilot data. The investigators expect that the effects will be larger than what is observed in pilot data because the latent variable approach will result in higher reliability measures.

Interim analysis

No interim analyses are planned.

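### No pre-exposure susceptibility score enters the primary analysis, which costs precision at Visit 4 but does not bias the randomised comparison

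*Protocol*

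**What the plan says.** Protocol, Measures: "Susceptibility to vaping at Visit 4 was the primary trial outcome". The instrument is described so: "We assessed susceptibility with a 3-item susceptibility to vaping scale, similar to other studies". It is the mean of three items scored 1 to 4. On timing: "Susceptibility was measured *after* ad exposure at Visit 1 to capture immediate ad impact and *before* ad exposure at Visits 2-4". The order of the Visit 1 survey agrees. Vaping and smoking behaviour come first, then the ads with the reaction items, "after which they completed measures of susceptibility to vaping and smoking, vaping and smoking beliefs, and demographics".

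Protocol, Participants: adolescents had to be "susceptible to e-cigarette use as shown by an answer of 2 or greater on any of five e-cigarette susceptibility items". The screening items use the same 1-to-4 response anchors as the outcome scale. The Protocol gives them no role beyond eligibility. Randomisation takes place at the start of Visit 1 (Procedures), so these answers precede it.

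SAP, Primary analyses: a linear growth model is fitted with its intercept at the last time point, and the intercept and slope are regressed on an arm indicator. No baseline or screening covariate is named. Under Sample size and power, the SAP gives an ICC of .7, a design effect of 2.4, up to 33% dropout and a detectable d of .25, and says: "The investigators will use a FIML estimator so the investigators can retain all available data".

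**The concern.** All four values of the primary outcome scale come after randomisation and after the first exposure. Stable differences between adolescents in how open they were to vaping at entry therefore stay in the error of the arm comparison. An ICC of .7 implies that most of the variation in susceptibility is of this stable kind, which is the situation in which a baseline covariate helps most.

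The Visit 1 score cannot fill the gap. It is taken after the ads in order to capture their immediate effect, so conditioning on it could remove part of the effect under study. The one vaping measure clearly placed before the first ad in the Visit 1 survey is vaping behaviour, which is a different construct.

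At stake is the standard error of the primary contrast, in a trial that already asks susceptibility questions before randomisation.

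**Working it through.** **The plan's own figure.** The design effect of 2.4 equals 1 + (3 − 1) × .7, so it corresponds to three measurements; four would give 1 + 3 × .7 = 3.1. The SAP states no power level, so d = .25 cannot be strictly reproduced. With a two-sided .05 test (sidedness assumed) and two intervention arms against one control arm, power at d = .25 is:

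- 83.8% for 1,500 participants divided by 2.4;
- 67.4% for 1,500 × .67 = 1,005 completers divided by 2.4;
- 96.2% for 1,005 completers (335 against 670) with no design effect.

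The value of a baseline is therefore given below as a ratio of standard errors, which does not depend on which basis was meant.

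**Inputs.** Four equally spaced visits with a linear trajectory and the intercept at Visit 4 (SAP). Total variance 1, split into .7 shared and .3 independent error (SAP's ICC). Dropout is 0 or 33% (SAP); its pattern is assumed, with 11% lost before each of Visits 2, 3 and 4. The correlation r between a pre-exposure score and each later visit is assumed.

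**No dropout.** The variance of the Visit 4 intercept per participant is .7 + .3 × (1/4 + 1.5²/5) = .7 + .3 × .70 = .91. Conditioning on the score removes r² from the shared part:

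- r = .3: .91 − .09 = .82; √(.82/.91) = .95, a cut of 5%.
- r = .5: .91 − .25 = .66; √(.66/.91) = .85, a cut of 15%.
- r = .7: .91 − .49 = .42; √(.42/.91) = .68, a cut of 32%.

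**33% dropout.** Generalised least squares over the dropout patterns gives a variance of 1.065 without the score, and .972, .807 and .550 with it at r = .3, .5 and .7. The standard error ratios are .96, .87 and .72, which are cuts of about 4%, 13% and 28%.

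**Cross-check on Visit 4 alone.** The residual variance factor is 1 − r². At r = .7 this is .51, and √.51 = .71, in line with the figures above.

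**Gain over the existing screening answers.** The cuts above are against no covariate. If the five-item screening mean were used and correlated .65, .60 or .50 with later visits (assumed), adding identical items at r = .70 would cut the standard error by a further 6%, 11% or 17% with 33% dropout. If the three items are among the five, the further cut is zero.

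**The case against.** The strongest reply is that a same-scale baseline may already be in hand. A reader might infer from the differing item counts that the outcome items are never asked before the first ad. The documents do not show this. The screening items share the outcome's response anchors and its stated construct of openness to vaping, the three may be among the five, and the item tables are in a supplement that is not provided. This stands, and the fix allows for it.

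Second, randomisation makes the Visit 4 comparison valid without a baseline. This also stands, and it rules out several stronger readings:

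- *Chance imbalance as a separate harm.* With 500 against 1,000 its standard error is √(1/500 + 1/1000) = .055 SD, but that uncertainty is already in the standard error of the contrast. Counting it again would count the same loss twice.
- *Immediate ad impact needs a before-value.* The control arm identifies it.
- *FIML fails for anyone who stops during the first ads.* With the baseline as a predictor, a person with no outcome value would still add essentially nothing to the arm effect. The documents give no figure for such early exits.

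Third, a reader might multiply the stated d = .25 by the ratios above to obtain a smaller detectable effect. That mixes bases. In the growth model used here, with 33% dropout and 80% power assumed, the detectable d without any baseline is already √1.065 × √(1/500 + 1/1000) × 2.80 = .16.

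Fourth, the timing is a reasoned choice, and asking identical items shortly before the ads could anchor the Visit 1 answer. That is a real but small cost. All participants already answer five susceptibility items at screening, and the scale is repeated at every visit.

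**Conclusion.** The point holds as a loss of precision. As described, no pre-exposure susceptibility score is used, although susceptibility items are answered before randomisation. Against no covariate, using one would reduce the standard error of the Visit 4 arm effect by 4-5%, 13-15% or 28-32% at r = .3, .5 or .7. The upper figure takes the SAP's ICC as a stand-in for r. Admitting only susceptible adolescents may lower r, and the lower figures would then apply. The gain specifically from collecting identical items is smaller than these cuts, and nil if the items overlap.

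The documents do not support a claim of bias in the primary contrast, nor a claim that the trial is underpowered for want of a baseline. The calculation assumes a linear trajectory, no slope variance, and dropout of the kind FIML handles.

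**What to change.** 1. Keep the pre-randomisation susceptibility answers as scores, not only as a pass or fail result, and state whether the three outcome items are among the five.
2. If they are, score their mean as the baseline. If they are not, add them to the screener in identical wording. The Protocol describes recruitment in the past tense, so this may no longer be possible; in that case use the mean of the five screening items.
3. Prespecify that score in the SAP as a predictor of the intercept and slope factors in the primary model.
4. State that the post-ad Visit 1 score is an outcome and will not be used as a baseline covariate. Leave the Visit 1 to 4 administrations as they are.

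The cost is one or two SAP sentences and at most three short items before randomisation. The downside is slight possible anchoring of the immediate Visit 1 response from repeated items, which all arms would see equally. If stored answers are used, nothing is added to the survey.

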**Impact of The Real Cost Vaping Prevention Advertisements on
Adolescents**

Hypotheses and Analytic Plan

NCT #04836455

Version Date: 4/23/2021

Hypotheses

The goal of this study is to determine whether exposure to vaping prevention advertisements reduce susceptibility to vaping. The **primary hypothesis** is that participants who view *The Real Cost* vaping prevention advertisements will have lower susceptibility to vaping compared to those who view neutral vaping control ads at 3 week follow-up.

The investigators also aim to examine the impact of *The Real Cost* vaping prevention ads on a series of other vaping-related outcomes. **Additional hypotheses** are that, compared to exposure to neutral vaping ads, participants exposed to *The Real Cost* vaping prevention ads will report the following at 3-week follow-up:

- Lower susceptibility to vaping
- Higher health harm risk beliefs about vaping
- Higher addiction risk beliefs about vaping
- More negative attitudes toward vaping
- Less vaping
- Higher attention (assessed only at 2-week follow-up)
- Higher negative affect (assessed only at 2-week follow-up)
- Higher cognitive elaboration
- More social interactions

The investigators will also explore the effects of *The Real Cost* vaping prevention ads on cigarette smoking-related outcomes, compared to exposure to neutral vaping ads. There are **not have directional hypotheses** for the following outcomes:

- Susceptibility to smoking cigarettes
- Health harm risk beliefs about smoking cigarettes
- Addiction risk beliefs about smoking cigarettes
- Attitudes towards smoking cigarettes
- Cigarette smoking behavior

Finally, the investigators will explore whether health harms vaping prevention ads out-perform addiction *The Real Cost* ads. We have labeled this an exploratory activity because the study is powered to compare these ads to control ads but not to one another.

Primary analyses

The investigators will use a critical alpha of 0.05 in all statistical tests. Analyses of the primary and secondary outcomes will include all randomized participants according to the trial arm they were randomized to receive (i.e., intent-to-treat). The investigators will use multiple imputation to handle any missing data on predictors and full information maximum likelihood to handle any missing data on outcomes.

The investigators will report univariate and bivariate descriptive statistics for the primary and secondary outcomes.

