For significance testing of the primary hypotheses, the investigators will compare those in *The Real Cost* trial arms (combined) to the control arm. The investigators will use latent curve models so that the investigators can model change in repeated measures over time. After establishing a linear growth trajectory for each latent construct with the intercept coded to be at the last time point, the investigators will regress the latent intercept and slope factors for each outcome on an indicator of random assignment to *The Real Cost* trial arms or to the control arm.

A significant effect on the intercept will indicate a main effect of treatment assignment on the mean level of each outcome at the last time point. A significant effect on the slope, if positive, will indicate that repeated viewing of the ads led to an increase in the difference across trial arms. If negative, it will indicate that the treatment effect diminished over time. As a secondary analysis, the investigators will examine whether there were significant differences in growth factor means as a function of assignment to the *The Real Cost* ad trial arms.

The investigators will also conduct the above analyses comparing those in the *The Real Cost* health harms trial arm to those in the *The Real Cost* addiction trial arm to explore whether there are differences across those trial arms.

The investigators will use a separate model for each of the study outcomes. To account for multiple comparisons, the investigators will use a Benjamini-Hochberg correction to maintain a 5% false detection rate.

Finally, the investigators will conduct exploratory moderation analyses on the primary outcome to examine whether the following variables moderate the impact of *The Real Cost* trial arms (compared to the control arm) on susceptibility to vaping: gender, age, race, Hispanic ethnicity, sexual orientation, parent's education, current vaper (vs. non-current vaper), and tobacco user in the household.

Sample size and power

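### Days vaped and days smoked are pre-ad baselines at Visit 1, but the SAP models them as outcomes on a four-visit line with free arm effects

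*Protocol*

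**What the plan says.** The Protocol (Procedures) describes "four weekly online visits over a three-week period" and says "Exposures to campaign ads occurred at Visits 1, 2, and 3". So the first ads are shown inside the Visit 1 session, and the Visit 2 survey comes before the second set.

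The Protocol (Measures) takes the vaping outcomes, including social interactions, once the ads have been shown at Visit 1 but ahead of the ads at later visits. Its timing sentence closes with this exception: "ad exposure at Visits 2-4, except for days vaped which was always measured before ad exposure". The opening paragraph of Measures has participants report both vaping and smoking behavior at Visit 1 before the ads, so days smoked has the same timing as days vaped. Both items count days of use over the past 7 days, so the Visit 1 window lies wholly before exposure.

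The SAP (Hypotheses) lists less vaping and "More social interactions" among its directional three-week hypotheses, and cigarette smoking behavior as exploratory. Under Primary analyses it says "The investigators will use a separate model for each of the study outcomes". The arm indicator enters "After establishing a linear growth trajectory for each latent construct with the intercept coded to be at the last time point", with an effect on both intercept and slope. The intercept effect is read as the difference at the last visit, and a positive slope effect is credited to seeing the ads again. No outcome has its Visit 1 value handled differently.

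**The concern.** For the two days-used outcomes, randomization fixes the expected Visit 1 arm difference at zero. The planned model ignores this in two ways.

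First, it estimates a difference that is already known and does not use Visit 1 to adjust the Visit 4 comparison.

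Second, it draws a straight line through a point that must be near zero. If the effect appears after the first viewing and then levels off, the line overshoots at Visit 4 and shows an upward slope. The plan would report that slope as a gain from repeated viewing, although one session had produced the whole effect.

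At stake are the size and interpretation of the behavioral results. The primary outcome is not affected: susceptibility is measured after the ads at Visit 1 on purpose, and the Protocol gives immediate impact as the reason.

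**Working it through.** **Inputs.** Four weekly visits, with time coded t = −3, −2, −1, 0 (Protocol, Procedures; SAP, intercept at the last visit). ICC .70, 500 per arm, up to 33% dropout (SAP, Sample size and power). The ICC is one general planning value and none is given for days used. I therefore use two structures as assumptions: compound symmetry (.70 at every lag) and AR(1) .70. The arm difference d is signed so that positive means a larger benefit.

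**The plan's own figure.** There is none on this point. The SAP's design effect reproduces as 1 + (3 − 1) × .70 = 2.4; only the ICC is used below.

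**Step 1: what the line does to each visit.** Mean t = −1.5 and Σ(t + 1.5)² = 5. Under compound symmetry:

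- Visit 4 weights, 1/4 + 1.5(t + 1.5)/5: −.2, .1, .4, .7
- Slope weights, (t + 1.5)/5: −.3, −.1, .1, .3

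Generalized least squares under AR(1) .70 gives −.109, .096, .135, .878 and −.329, −.013, .013, .329.

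**Step 2: apply the weights to arm differences that are zero at Visit 1.** For the step under compound symmetry, Visit 4 = (.1 + .4 + .7)d = 1.20d and slope = (−.1 + .1 + .3)d = .30d.

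| True difference, Visits 1 to 4 | True Visit 4 | Compound symmetry: Visit 4, slope | AR(1): Visit 4, slope |
|---|---|---|---|
| 0, d, d, d (step) | d | 1.20d, +.300d | 1.109d, +.329d |
| 0, .5d, d, d | d | 1.15d, +.350d | 1.061d, +.335d |
| 0, d/3, 2d/3, d (ramp) | d | 1.00d, +.333d | 1.00d, +.333d |
| 0, d, 2d/3, d/3 (fading) | .333d | .60d, +.067d | .479d, +.105d |
| 0, 0, 0, 0 | 0 | 0, 0 | 0, 0 |

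In the fading case the effect falls from Visit 2, yet the fitted slope is positive. Random intercept-and-slope covariances give the same values as compound symmetry. With 33% dropout under compound symmetry, the step gives 1.231d (slope .325d) if losses are spread evenly and 1.135d (slope .309d) if all follow Visit 1.

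**Step 3: how often the step's slope would be called significant.** Take d = .25 and 500 × .67 = 335 control against 670 combined completers. Under compound symmetry the slope is .30 × .25 = .075, with SE = √[(.3/5)(1/335 + 1/670)] = .0164. Two-sided power at .05 is .996. Under AR(1) the slope is .082, the SE .0256 and the power .896. So a difference that is flat from Visit 2 would be reported as a slope effect about 90% to over 99% of the time.

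A point on sign: for days used, benefit is a decrease, so the raw slope coefficient would be negative. The SAP's sign rule, read literally, would call that a diminishing effect. The reading above assumes that the sign is oriented to benefit.

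**Step 4: precision of the Visit 4 contrast** (in units of σ²(1/n₀ + 1/n₁), complete data).

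- Planned model, compound symmetry: .7 + .3(1/4 + 1.5²/5) = .91.
- Visit 1 difference fixed at zero with visit-specific effects: 1 − ρ², where ρ is the correlation between Visits 1 and 4. This is 1 − .70² = .51, a variance 44% lower (SE ratio √(.51/.91) = .75).
- AR(1) .70: planned .982. With the baseline, ρ = .70³ = .343 and 1 − .343² = .882. This is 10% lower (SE ratio .95).

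If all 33% dropout follows Visit 1, the planned variance under compound symmetry is 1.150 and the baseline version is .51/.67 = .76, so most of the gain survives under that structure.

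**The case against.** Four objections deserve an answer.

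*Social interactions.* A reader might infer that the Visit 1 social-interactions score must also show no arm difference, because it is taken in the session of the first viewing. The documents do not support this. They describe a three-item scale and give neither the items nor the recall window. If the items ask about intended talk at every visit, an immediate effect is possible, as for susceptibility. This objection stands.

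*Size of the bias.* A reader might take 20% as the amount by which Visit 4 effects will be overstated. That is one profile under one covariance. With three weekly exposures a gradual build-up is plausible, and a straight ramp gives exactly 1.00d. Nor does the argument show false positives for an overall effect: with no effect at any visit, intercept and slope are both unbiased at zero.

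*Linearity is to be established first.* This might expose misfit, but the SAP gives no criterion and no fallback. An adequate overall curve also need not mean that the arm difference is linear.

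*Free estimation of a zero is not an error.* This is correct when the later effect is a ramp; the loss is then precision only. The 44% figure needs a correlation of .70 between Visits 1 and 4, and correlation that decays with time leaves about 10%.

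**Conclusion.** The point holds for days vaped and days smoked, where the documents settle the timing and no assumption about item wording is needed. The planned model forgoes a usable baseline. It misstates the Visit 4 effect when that effect does not rise in a straight line from Visit 1: by about +11% to +23% for a step over the covariance and dropout cases tried, and by more, proportionally, for a fading effect. The slope then cannot be attributed to repeated viewing. The complete-data precision gain from using the baseline is 10% to 44% of the variance, resting on an ICC of .70 that was not derived for these outcomes.

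For social interactions the point is conditional on items about past talk. It concerns effect size and interpretation for secondary and exploratory outcomes, not the primary result or type I error under a true null.

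**What to change.** 1. **Days vaped and days smoked.** State in the SAP that Visit 1 is a pre-exposure baseline. Either enter it as a covariate, or keep it in the full-information likelihood model with its arm difference fixed at zero. Estimate the Visit 4 contrast with visit-specific arm effects. Assess any build-up by comparing the Visit 4 and Visit 2 effects, not by a slope anchored at Visit 1.

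2. **Social interactions.** State the item wording and recall window at each visit. If all visits ask about past talk, use the same zero-difference constraint. If Visit 1 asks about intended talk and later visits about past talk, Visit 1 is a different construct and should not enter the curve as the same outcome.

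3. **Do not simply drop Visit 1 where it is a true zero.** That would lose everyone who leaves after Visit 1, against the SAP's intent-to-treat statement and its reason for choosing full-information likelihood. Under compound symmetry with 33% dropout, a line through Visits 2 to 4 raises the SE relative to the planned model by about 7% if losses are even (variance 1.065 to 1.212) and 11% if all follow Visit 1 (1.150 to 1.418).

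The cost is SAP wording and two or three model specifications, with no new data. The single slope summary is given up for these outcomes. The Protocol describes recruitment as complete, so if outcome data have been examined, report this analysis beside the planned one and label it as added.
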